#### 3.2 Study Groups

A total of 500 participants will be enrolled to receive the vaccine. All participants will be monitored for solicited adverse events for 7 days, unsolicited adverse events for 28 days, SAEs and MAEs for the one year duration of the study, and antibody measurements at baseline, Day 28, Day 84, week 24, and week 52. A subset of 50 participants will have cellular immunity measured at those same intervals.

This protocol amendment provides for unblinding of participants who were entered into the study in the double-blind schedule. For participants who entered the double-blind schedule, the visit process will be as follows:

a) Sites will receive an unblinding list detailing participants who received placebo or study vaccine. Participants who received placebo will be invited to continue in the study under the

open-label study scheme and should make visits from V1.B (first vaccine) onwards, after signing the informed consent, completing visits on day 28 (V2.B), day 56 (second dose) (V3.B), day 84 (V4.B), week 24 (V5.B) and week 52 (V6.B). In this group of participants already enrolled, no antibody dosage collection will be performed at the V1B visit; the V1 values at study entry will be taken. The letter B is added to the visits to differentiate this group of participants who must reorganize the schedule of visits from the administration of the first dose of CoVID vaccine after the unblinding. The procedures for this group are detailed in Table 2.

b) Participants who, after the unblinding, are found to have received study vaccine at the initial visit, will complete the visits established by protocol together with the administration of dose 2 of the study (day 56) onwards, after signing the informed consent. In this group of participants there will be no changes in the nomenclature of the visits.

For both arms (placebo and study vaccine), efficacy contacts are restarted with the second injection visit.

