#### **8.2 Participant withdrawal**

Participants who are withdrawn because of SAEs/AEs must be clearly distinguished from participants who are withdrawn for other reasons. Investigators will follow participants who are withdrawn as result of a SAE/AE until resolution of the event. Withdrawals will not be replaced, unless the withdrawal is prior to the first dose of study vaccine.

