#### **Participant withdrawal from the study**

From an analysis perspective, a ‘withdrawal’ from the study refers to any participant who did not come back for the concluding visit/was not available for the concluding contact foreseen in the protocol.

All data collected until the date of withdrawal/last contact of the participant will be used for the analysis.

A participant is considered a ‘withdrawal’ from the study when no study procedure has occurred, no participant contact has been performed and no further information has been collected for this participant from the date of withdrawal/last contact.

Investigators will make an attempt to contact those participants who do not return for scheduled visits or participant contact.

Information relative to the withdrawal will be documented in the eCRF. The investigator will document whether the decision to withdraw a participant from the study was made by the participant, or by the investigator, as well as which of the following possible reasons was responsible for withdrawal:

- SAE
- Non-serious AE
- Protocol violation (specify)
- Consent withdrawal, not due to an AE\*
- Moved from the study area.
- Lost to participant contact.
- Other (specify).

*\*In case a participant is withdrawn from the study because he/she has withdrawn consent, the investigator will document the reason for withdrawal of consent, if specified by the participant, in the eCRF.*

Participants who are withdrawn from the study because of SAEs/AEs must be clearly distinguished from participants who are withdrawn for other reasons. Investigators will follow participants who are withdrawn from the study as result of a SAE/AE until resolution of the event.

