## 9. OUTCOME MEASURES AND STATISTICAL METHODS

### 9.1 Sample Size Estimation

Since this is an open, non-comparative study that seeks to observe the impact of vaccination on the evolution of HIV disease, a sample size defined by statistical criteria is not established.

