### 9.2 Study Population and Analysis Sets

#### 9.2.1 Study Population

##### Intent-to-Treat Cohort

The intent-to-treat cohort consists of all participants who receive at least one study injection, regardless of their protocol adherence and continued participation in the study. Participants will be analyzed according to their randomized treatment. Participants who withdraw from the study will be included up to the date of their study withdrawal.

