### **9.3.3 Safety Analysis**

#### **Primary Safety Endpoint:**

- The incidence of solicited adverse reactions within 7 days after vaccination.
- The incidence of unsolicited adverse events within 28 days after vaccination.
- The incidence of detectable viral load 24 and 52 weeks after vaccination
- The incidence of serious adverse events (SAE) and medically attended adverse events (MAE) within 52 weeks after vaccination in all participants.

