#### **Secondary Safety Objective Endpoints**

- The incidence of a decrease in CD4+ cell count by  $\geq 20\%$  at 24 and 52 weeks after vaccination
- The delta in the CD4/CD8 rate compared to the basal value.

All SAEs will be listed and summarized by groups.

For each participant, the individual local events will be aggregated into a combined event "Local", which is the maximum severity of the individual local events. For each participant, the individual general events will be aggregated into a combined event "General", which is the maximum severity of the individual general events. An aggregate event "Any" will be defined as the maximal severity of the combined events "Local" and "General". In addition to being graded for severity as mild, moderate or severe, the severity of all events will be graded as "Any", which will include mild, moderate or severe events, and "Significant" which will include moderate or severe events.

All statistical tests on safety performed will be 2-sided with Type I error of 5%. Missing values will not be included in the safety analyses, and there will be no imputation of missing values. No adjustments will be made for multiple comparisons.

For the analysis of proportions, binomial point estimates and exact binomial confidence intervals will be calculated.

Fisher's Exact Test will be used to assess differences in rates of adverse events between treatment and control groups.

In addition, all safety data will be analysed descriptively, including unsolicited events collected through the end of the observation period.

The Safety analysis will be performed based on the intent-to-treat cohort and per-protocol cohort.

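### The only estimator named for the primary 52-week SAE and MAE incidence is a crude binomial proportion, which does not estimate 52-week risk once participants withdraw early; this matters for common MAEs, little for rare SAEs

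*Protocol*

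**What the plan says.** Section 9.3.3 lists among the primary safety endpoints: "The incidence of serious adverse events (SAE) and medically attended adverse events (MAE) within 52 weeks after vaccination in all participants". For the safety analysis it then states: "For the analysis of proportions, binomial point estimates and exact binomial confidence intervals will be calculated". It names no person-time or time-to-event method for SAEs or MAEs.

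On incomplete follow-up, the protocol has four rules:

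- Section 9.2.1 puts everyone with at least one injection in the intent-to-treat cohort and adds: "Participants who withdraw from the study will be included up to the date of their study withdrawal".
- Section 8.2 agrees: "All data collected until the date of withdrawal/last contact of the participant will be used for the analysis".
- Section 8.2 also says: "Withdrawals will not be replaced, unless the withdrawal is prior to the first dose of study vaccine".
- Section 9.3.3 says: "Missing values will not be included in the safety analyses, and there will be no imputation of missing values".

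Section 3.2 gives the size: "A total of 500 participants will be enrolled to receive the vaccine". Section 9.1 says that "a sample size defined by statistical criteria is not established", and the protocol states no expected event rate or withdrawal rate.

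**The concern.** A binomial proportion with an exact interval is right when each participant is observed for the whole risk period and is known to have had the event or not. That is nearly so for the 7-day and 28-day endpoints. Over 52 weeks it fails for anyone who leaves early without an event, because that person's 52-week outcome is unknown.

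The protocol does not say how such a person is counted. Section 9.2.1 points to keeping the person in the denominator, which treats a partial year as a full event-free year. The missing-value rule in section 9.3.3 can be read as removing the person, which discards event-free time at risk while withdrawals who had an event are kept. The two readings err in opposite directions.

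At stake is the long-term safety figure of a trial whose stated purpose (section 1.3) is to supply safety data for people living with HIV, and whether the interval around that figure has its nominal coverage.

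**Working it through.** The protocol contains no planned incidence, precision or dropout figure, so there is nothing to reproduce. What follows is a sensitivity calculation.

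**Inputs from the protocol.** N = 500 (section 3.2); a 52-week risk period (section 9.3.3); a binomial proportion with exact interval (section 9.3.3); withdrawals kept up to withdrawal and not replaced after the first dose (sections 8.2 and 9.2.1).

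**Assumed inputs.** True 52-week risk *p*; share withdrawing *d*; withdrawal times uniform over the 52 weeks and unrelated to event risk; constant hazard; a 95% level for the exact interval, in line with the two-sided 5% tests in section 9.3.3.

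**Formulas**

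- Hazard over the year: λ = −ln(1 − p).
- Chance that a withdrawn participant's event is seen before withdrawal: r = 1 − p/λ.
- Reading A, all dosed participants in the denominator: q_A = (1 − d)p + d·r.
- Reading B, event-free withdrawals removed: q_B = q_A / [(1 − d) + d·r].
- Coverage: the probability, under Binomial(500, q_A), that the Clopper-Pearson interval contains *p*.

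**Worked case, p = 20%, d = 10%.** λ = 0.2231. r = 1 − 0.2/0.2231 = 0.1037. q_A = 0.9 × 0.20 + 0.1 × 0.1037 = 0.1904. q_B = 0.1904 / (0.9 + 0.0104) = 0.2091.

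| True risk | Withdrawal | Reading A | Coverage under A | Reading B |
|---|---|---|---|---|
| 3% | 10% | 2.85% | 96.4% | 3.16% |
| 3% | 20% | 2.70% | 95.5% | 3.36% |
| 10% | 10% | 9.51% | 95.1% | 10.5% |
| 10% | 20% | 9.02% | 91.1% | 11.1% |
| 20% | 10% | 19.0% | 92.3% | 20.9% |
| 20% | 20% | 18.1% | 81.9% | 22.0% |
| 40% | 10% | 38.2% | 87.1% | 41.4% |
| 40% | 20% | 36.3% | 61.5% | 43.1% |

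Under reading A the relative bias is close to d/2. With no withdrawal the exact interval covers slightly more than 95% (96.5% at a true risk of 3%, 95.6% at 20%, 95.5% at 40%), and this reserve absorbs a small bias. Coverage first drops below 95% at about 24% withdrawal for a true risk of 3%, 11% for 10%, 5% for 20% and 3% for 40%.

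**Sensitivity to timing, reading A**

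- Half of all events by Day 84, p = 40%, d = 10%: estimate 38.5%, coverage 90.1%.
- All withdrawals at Day 0, p = 40%, d = 10%: estimate 36.0%, coverage 55.4%.
- All withdrawals at Day 0, p = 3%: estimate 2.70% with coverage 95.5% at d = 10%, and 2.40% with coverage 91.2% at d = 20%.

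**The case against.** The strongest reply is that this belongs to the statistical analysis plan. Section 9.3 defers method details to it, the quoted sentence is generic to proportions, and nothing in it forbids a person-time or Kaplan-Meier summary. The study is open and non-comparative, no threshold or suspension criterion uses the 52-week proportion, and the share of vaccinated participants with a reported event is a legitimate description. Part of this stands: a later document may add the better estimate, and the crude count deserves to be reported. But section 9.3.3 already fixes the estimator and the missing-value rule, and a plan that follows both as written does not estimate 52-week risk under either denominator.

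The reply is also right that the calculation may overstate the bias. Section 8.2 counts anyone who misses the concluding visit or contact as a withdrawal, even with nearly a full year observed. SAE and MAE collection is largely remote, which helps retention. MAEs may cluster after the doses, and the early-event case above shows a smaller bias.

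Four stronger readings are tempting, and the documents do not support them:

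- **The estimate must be too low.** This holds only with all dosed participants in the denominator. Removing event-free withdrawals reverses the sign, and informative withdrawal could shift the bias either way.
- **The exact interval under-covers in general.** It does not for SAE-like risks of about 3% with even withdrawal up to 20%. Nothing in the protocol suggests SAE risks of 20% to 40%; its background reports no SAE within 28 days in phase I or phase II, although that window is short.
- **Section 1.3 shows that early exit should be expected.** Its remark on national vaccination concerns reduced access to the placebo-controlled design, not departure from the study, and all participants now receive active vaccine.
- **Events of withdrawn participants would be lost.** Section 8.2 keeps all data up to last contact. What reading B loses is event-free time at risk.

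**Conclusion.** The concern holds in a limited form. The estimator named for the primary 52-week SAE and MAE endpoint does not match the follow-up that the protocol itself describes, and the denominator for early event-free withdrawals is unclear. That mismatch follows from the text and is well established.

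The size is conditional, because the protocol states neither an event rate nor a withdrawal rate. Under non-informative, evenly spread withdrawal of 10% to 20%, with all dosed participants counted, the effect is negligible for rare SAEs. It is material for MAEs if these are common, at true risks of about 20% or more. The definition of an MAE, an adverse event requiring contact with health care, makes such risks plausible over a year, but they remain an assumption. The point warrants a change of estimator; it does not show that the reported incidence will be wrong in a known direction or by a known amount.

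**What to change.** For the 52-week SAE and MAE endpoints, specify in section 9.3.3:

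- the Kaplan-Meier (cumulative incidence) estimate at Week 52 with its 95% confidence interval, censoring at last contact;
- events per person-year;
- the crude count over all dosed participants, with that denominator stated.

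Also state that the missing-value rule does not remove participants with partial follow-up from these endpoints. Keep the exact binomial intervals for the 7-day solicited and 28-day unsolicited endpoints.

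The cost is minor programming. SAEs and MAEs are already recorded in the eCRF, and section 8.2 already relies on the date of withdrawal or last contact. The drawback is that the Kaplan-Meier estimate assumes non-informative censoring. Listing the reasons for withdrawal, which section 8.2 already collects, beside the estimate lets a reader judge that assumption.

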In its original version, the protocol limited inclusion to "people living with HIV on stable treatment and virologically suppressed..." .

Likewise, the design was double-blind versus placebo in a 2:1 ratio.

The advancement of the national vaccination reduced the possibilities of access to the study under such design, for which this protocol amendment was proposed.

Volunteers initially included in the study will receive two doses of the vaccine and will continue their follow-up as established in the protocol.

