#### Time period for detecting and recording adverse events and serious adverse events

All AEs starting within 28 days following administration of the dose of the study product must be recorded into the appropriate section of the eCRF, irrespective of intensity or whether or not they are considered injection related.

The time period for collecting and recording SAEs and MAEs in all participants will begin at the first receipt of study product/comparator and will end on Day 364.

All AEs/SAEs leading to withdrawal from the study will be collected and recorded from the time of the first receipt of study product. SAEs that are related to the investigational product will be collected and recorded from the time of the first receipt of study product/comparator until the participant is discharged from the study.

In addition to the above-mentioned reporting requirements and in order to fulfill international reporting obligations, SAEs that are related to study participation (i.e. protocol-mandated procedures, invasive tests, a change from existing therapy) will be collected and recorded from the time the participant consents to participate in the study until she/he is discharged from the study.

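### The amended trial is open and non-comparative, but its analysis text still uses randomised arms, tests treatment against control, and names only a between-group test for seroconversion after one versus two doses

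*Protocol*

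**What the plan says.** **Design.** Section 9.1 gives the reason for having no statistical sample size: "Since this is an open, non-comparative study that seeks to observe the impact of vaccination on the evolution of HIV disease". Sections 3.1 and 3.2 schedule a first Ad5-nCoV dose at entry and a second at Day 56 for all 500 participants. Section 1.3 records the former design: "Likewise, the design was double-blind versus placebo in a 2:1 ratio". Section 3.2 then states: "This protocol amendment provides for unblinding of participants who were entered into the study in the double-blind schedule". It adds: "Participants who received placebo will be invited to continue in the study under the" open-label scheme, with two vaccine doses on a relabelled visit schedule.

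**Analysis of safety.** For the intent-to-treat cohort, Section 9.2.1 states: "Participants will be analyzed according to their randomized treatment". Section 9.3.3 and the synopsis set tests at two-sided 5% and say that Fisher's "Exact Test will be used to assess differences in rates of adverse events between treatment and control groups". The same text also gives binomial estimates with exact confidence intervals, which need no control. The exploratory items (synopsis, Sections 2.2.4 and 9.3.5) keep a comparison of COVID-19 severity with a control group.

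**One versus two doses.** This is a primary immunogenicity objective in Section 2.1 and a primary endpoint in Section 9.3.4 and the synopsis endpoint list. The synopsis objective mentions two doses only. For rates, Section 9.3.4 and the synopsis name a Fisher test between groups. For geometric means they name t-tests, without saying whether these are paired.

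**The concern.** The analysis rules describe a randomised two-arm trial that the amended protocol no longer runs. Read literally, the intent-to-treat rule keeps former placebo recipients in the placebo arm after they have received two vaccine doses, so their vaccine-period events can be attributed to placebo. Participants enrolled after the amendment have no randomised arm. A treatment-versus-control p-value from such a table would have no clear meaning.

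The one-versus-two-dose endpoint raises a separate problem. No one-dose group is planned, so the scheduled contrast is within each person: Day 28 (28 days after dose 1) against Day 84 (84 - 56 = 28 days after dose 2). A between-group Fisher test treats the two samples from one person as two unrelated people. With positive within-person correlation it is conservative and loses power, here on a primary endpoint.

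**Working it through.** The protocol states no power, effect size or statistically derived sample size, so there is no figure to reproduce. The check compares the texts and then gives illustrations on stated assumptions.

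**1. Can a control group exist?**
- Under the current design, the planned control size is 0 of 500.
- The former placebo group is the only candidate. Its size and its uptake of vaccine are not given.
- Neither the randomised-arm rule nor the Fisher test is limited to the period before unblinding.
- For SAEs and medically attended events, Section 7.2 says that collection "will begin at the first receipt of study product/comparator and will end on Day 364". For a former placebo recipient, read literally, that clock starts at the placebo injection.
- The solicited endpoint is written as "The incidence of solicited adverse reactions within 7 days after vaccination". It does not say how several injections in one person are combined.

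**2. How much could a difference be diluted?** Inputs: injection-site pain v = 56% per dose at this dose level (Section 1.2; healthy adults, a 14-day figure, whereas the endpoint here is 7 days). Assumed: placebo rate q = 5% to 20%; arms of 60 v 30 or 120 v 60; independent injections; exact two-sided Fisher at 5%.
- Blinded phase only: 56% v 5% to 20%, a difference of 36 to 51 points; power 92% to 100%.
- Full crossover, with each person counted as ever reacted over all injections: vaccine arm 1 - (1 - 0.56)² = 81%; placebo-randomised arm 1 - (1 - q)(0.44)² = 82% to 85%; rejection 3.6% to 7.5%.
- Uptake a, same pooling: placebo-arm rate (1 - a)q + a[1 - (1 - q)(0.44)²]. At a = 75% this is 62.5% to 68.4%, 12 to 18 points below the vaccine arm; rejection 21% to 71%. At a = 50% it is 43.3% to 52.3%, 28 to 37 points below; rejection 76% to 99.9%.
- Full crossover, counted per injection: (q + 2v)/3 = 39% to 44% v 56%. First injections alone keep 56% v 5% to 20%.

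The effect therefore runs from near-complete masking to none, depending on two things that the protocol does not state.

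**3. One versus two doses, rates.** Assumed: 500 complete pairs, 90% at Day 28, 94% at Day 84, within-person correlation φ. The proportion positive at both visits is 0.90 × 0.94 + φ√(0.90 × 0.10 × 0.94 × 0.06). At φ = 0.5 this is 0.846 + 0.036 = 0.882, so the discordant proportions are 0.018 and 0.058. Simulated power at φ = 0.3, 0.5, 0.7:
- Fisher: 63%, 66%, 69%
- Exact McNemar: 76%, 89%, 99%

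These vary by about a point between simulation runs. The result depends on the rates:
- From 47% (neutralising seroconversion at Day 28, Section 1.2) to an assumed 53%: Fisher 44% to 46%, McNemar 60%, 75%, 93%.
- From 97% (the RBD ELISA figure at Day 28, Section 1.2) to an assumed 98%: McNemar itself reaches only about 16% to 30%.

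**4. Geometric means, only if the t-test were unpaired.** The standard error is too large by 1/√(1 - ρ) = 1.20, 1.41, 1.83 at ρ = 0.3, 0.5, 0.7. True alpha is 2[1 - Φ(1.96/√(1 - ρ))] = 1.9%, 0.6%, 0.03%.

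**5. What is unaffected.** Single-arm exact 95% intervals at N = 500: 0 events gives 0 to 0.74%; 75 events gives 12.0% to 18.4%.

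**The case against.** **A legitimate control existed before unblinding.** True. A comparison by randomised arm up to unblinding would be valid, but no text restricts the rule or the test to that subset and period.

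**Details are left to the SAP.** Section 9.3 says so, and paired or unpaired t-tests are a normal SAP detail. The t-test point therefore rests on silence and is not claimed as an error. The analysis by randomised arm, the treatment-versus-control test and the between-group Fisher test for rates are stated outright, and a SAP that follows them inherits the problem.

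**Groups could mean baseline-antibody strata.** The synopsis and Section 5.1 plan a stratified sub-analysis, so this is possible for immunogenicity. Section 9.3.4 does not say so, and strata cannot be the treatment and control groups of Section 9.3.3.

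**A reader might infer that vaccine reactogenicity would be hidden.** The documents do not support that. Masking needs near-full crossover and pooling of placebo and vaccine injections into one indicator per person, and neither is stated. The synopsis counts unsolicited events after each vaccination, each vaccine dose has its own diary, and crossover visits carry separate labels. The single-arm incidences and the SAE listing remain in any case.

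**The paired test may not rescue the endpoint.** Near 97% after one dose it would not give useful power. Whether people with HIV respond that strongly is unknown here. This limits the gain but does not make an independent-samples test right for paired rates.

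**Conclusion.** The contradiction is in current text and should be fixed before analysis. The between-group safety layer has no defined control under the amended design and is not interpretable as written. The size of any dilution cannot be fixed from the protocol. The primary one-versus-two-dose endpoint lacks a within-person method for rates; the named test errs on the conservative side. The power loss is about 7 to 30 points under the 90% v 94% illustration (76 - 69 at the closest pairing of the two ranges, 99 - 69 at correlation 0.7) and depends on assumed rates and correlation.

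Two stronger conclusions are not supported: that reactogenicity will be concealed, and that the t-tests are unpaired. The single-arm safety estimates and the descriptive exploratory listings stand.

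**What to change.** 1. **Section 9.2.1.** Define the main set as all participants with at least one Ad5-nCoV dose, with time counted from the first Ad5-nCoV dose. Former placebo recipients need a specific rule. Section 3.2 reuses their entry antibody values, and Table 2 schedules no viral-load or CD4 sample at V1.B. State that entry values are reused for all three. Report immunogenicity and HIV-marker results with and without these participants, because infection or change during the placebo period would otherwise count as a vaccine effect.
2. **Section 9.3.3 and the synopsis safety text.** Delete the treatment-versus-control Fisher test and keep the single-arm estimates with exact intervals. Alternatively, confine any randomised comparison to blinded-phase participants, by randomised arm, up to unblinding.
3. **Section 9.3.4 and the synopsis immunogenicity text.** Specify one versus two doses as a paired Day 28 versus Day 84 comparison: McNemar for seroconversion, paired t-test on log10 titres. State that dose number and time since first dose are confounded. Limit this endpoint to those two visits, because Weeks 24 and 52 have no scheduled one-dose counterpart. Do not use participants who miss dose 2 as a comparison group, because they are a selected subset (Sections 6.2 and 8.2). Align the synopsis objective with Section 2.1, Section 9.3.4 and the synopsis endpoint.
4. **Synopsis, Sections 2.2.4 and 9.3.5.** Restate the control-group severity item as severity among vaccinees.

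The cost is protocol and SAP wording, with no new visits or samples. The trial gives up a comparison that the open design cannot deliver; a blinded-phase comparison remains possible but may be small and short.
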